## **C. Considerations for Improved Subject Selection for the Current Proposal**

In our clinical and research experience vestibular attacks can be reliably identified and should be the easiest of all VM symptoms to target for treatment. The most frequent duration of vestibular attacks with VM is hours to a few days. Focusing on patients with this duration of attacks is logical to maximize recruitment and ensure that enrolled subjects have attacks of sufficient duration to assess response to treatment. Therefore, our cohort of interest will be patients with a lifetime histories of five or more vestibular attacks lasting 2-72 hours with full interictal recovery and diagnoses of migraine. With regard to comorbidities, the requirement for at least five spontaneous episodes without hearing loss over more than a year will effectively exclude early cases of Meniere's syndrome. Patients with previously established Meniere's disease will be excluded from this study because their acute vertiginous symptoms overlap considerably with those of VM. Vertigo attacks caused by BPPV are of short duration (<2 minutes), making them easy to distinguish from the hours-long attacks of VM in our cohort of interest. CSD causes chronic non-vertiginous symptoms, not episodic symptoms. Therefore, patients with coexisting BPPV or CSD will not be excluded if they have vestibular attacks and meet all other inclusion and exclusion criteria. Coexisting anxiety or depressive disorders will be managed during the observation period and will not be exclusionary, if they can be stabilized within three months. These considerations balance the needs for successful subject recruitment, subject safety, and focus on the target symptoms of interest (i.e., recurrent, spontaneous vestibular attacks in patients with VM), while retaining generalizability to real world clinical settings and gathering critical information about potentially confounding variables for future Phase III trials, all informed by our preliminary data and previous clinical experience.

## D. Summary of Innovation

Two important improvements over previous work have been incorporated into this proposal. The first innovation is a practical one in terms of study design. We carefully considered shortcomings in the previously published zolmitriptan trial and incorporated design elements into this proposal to overcome them, including enhanced subject selection criteria, a prospective observation period, and specific strategies for addressing the common problem of comorbidity in VM (essentially ignored in previous studies). If we are successful, then these elements will inform the design of future therapeutic investigations for patients with VM, including not only Phase III studies of rizatriptan, but also clinical trials of other abortive and prophylactic therapies.

The second innovation concerns the fundamental definition of VM. We will use the recently published ICHD-3 diagnostic criteria as they represent the current consensus of international experts in the field, although they have not yet been formally validated. We will focus our intervention specifically on recurrent spontaneous vestibular attacks lasting at least 1 hour in the absence of auditory deficits. We will require that enrolled subjects have at least 2 qualifying vestibular attacks during the observational phase so that we can teach them when and how to treat attacks in a systematic and consistent manner before they enter the treatment phase. If we are successful, our results will support the concept of VM as defined by the new criteria.

## III. APPROACH

We propose a two-center, randomized, double blind, placebo-controlled, parallel, three-episode, clinical trial of rizatriptan 10 mg oral tablets versus placebo for treating spontaneous vestibular attacks in patients with VM.

Our primary Specific Aim is to test hypotheses 1a-1d that rizatriptan will be:

- 1a. Superior to placebo in reducing the severity and duration of vestibular attacks as measured by:
  - (1) Proportion of treated attacks in which subjects experience a reduction in severity rating from Grade 3/2 to Grade 1/0 at one hour after taking study medication (see below for rating description). This is the main outcome measure; 1a(2)-1d(2) are secondary outcome measures.
  - (2) Proportion of treated attacks in which subjects achieve sustained relief (i.e., vestibular symptom severity rating of Grade 1/0) for 24 hours after taking study medication, without use of non-study therapies.
  - (3) Proportion of treated attacks in which subjects experience freedom from vestibular symptoms (i.e., severity rating of Grade 0) at one hour after taking study medication.
  - (4) Use of fewer non-study therapies after each attack treated with study medication.
- 1b. Superior to placebo in reducing severity of symptoms associated with vestibular attacks as measured by:
  - (1) Proportion of treated attacks in which subjects experience relief (reduction to Grade 1/0) from VM-associated symptoms (e.g., nausea, vomiting, motion sensitivity, gait disturbance, headache, photophobia, and phonophobia) at one hour after taking study medication.
  - (2) Proportion of treated attacks in which subjects achieve sustained relief from VM-associated symptoms for 24 hours after taking study medication without use of non-study therapies.
- 1c. Superior to placebo on treatment satisfaction and health-related quality of life as measured by:
  - (1) Scores on the Treatment Satisfaction Questionnaire for Medication (TSQM) at 48 hours after each attack treated with study medication
  - (2) Scores on the Short Form 12 (SF-12) at 48 hours after each attack treated with study medication
- 1d. Tolerated as well as placebo by patients with VM as measured by:
  - (1) No greater rate of treatment-emergent serious adverse events reported on the NCI Common Toxicity Criteria Scale 4.0^59 obtained 48 hours after each attack treated with study medication.
  - (2) No greater rate of treatment discontinuation for adverse events of any type or severity.

Our secondary Specific Aim is to gather data that will be needed to establish rigorous inclusion and exclusion criteria, determine sample sizes, and prepare Manuals of Operating Procedures for future Phase III treatment trials of rizatriptan and other abortive and prophylactic medications for VM. We intend to gather the following specific information during the Observation Phase of this study, which will last up to 12 months:

- 2a. The natural range of frequency and severity of vestibular attacks in treatment-seeking patients with VM.

Our goal is to identify the mean, median, and range of naturally occurring vestibular attacks in patients with VM, allowing future investigators to accurately estimate the sample sizes and study durations needed for abortive and prophylactic medication trials.

2b. The type and severity of medical and psychiatric conditions that commonly coexist with VM. Our goal is to identify the prevalence and severity of common comorbidities of VM, allowing future investigators to make informed decisions about the inherent compromise between excluding subjects with potential confounds versus including subjects with manageable comorbidities to maintain real world generalizability.

2c. The types, doses, and frequency of use of prescription and non-prescription medications for VM. Our goal is to create a compendium of usual clinical care and self-treatment of VM, giving future investigators naturalistic data to (1) guide selection of allowable co-treatments in future studies of prophylactic and abortive medications for VM and (2) determine which usual care treatments may be worthy of future controlled trials.

We also intend to collect the data described in 2a-c through the treatment phase of the study. Our goal is to conduct exploratory analyses of the influence of these variables on the efficacy of rizatriptan for VM, further enhancing the design of future Phase III trials and providing possible insights into the pathophysiology of VM

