**2. Observation Phase.** Subjects will be followed for up to 12 months to prospectively characterize the frequency and severity of their vestibular attacks, associated symptoms, and comorbid conditions. Subjects will record data about all vestibular attacks that they experience during this period in their Vestibular Symptom Diaries (see description below). Subjects will be permitted to treat their symptoms according to usual clinical care. They will record all interventions in their Vestibular Symptom Diaries. Study personnel will review this information with subjects by telephone on a monthly basis and will inquire about interval changes in subjects' health and medications. This process will build rapport with subjects, ensure that they continue to meet inclusion/exclusion criteria, and identify comorbid conditions that could affect their safety or subsequent study treatment. Study personnel also will use these data to train subjects to reliably recognize attacks that will be appropriate for treatment with study medication when they enter the Treatment Phase of the investigation. Treatable comorbidities (e.g., mild hypertension, anxiety disorders) will be managed in coordination with subjects' primary care clinicians or relevant specialists. Patients whose comorbidities cannot be managed and patients who do not have two qualifying episodes after 12 months of observation will be disenrolled.

**3. Visit 2.** As soon as possible after subjects have their second qualifying attack, they will return to the study sites for re-evaluation. They will complete procedures in Table 2. Investigators will instruct subjects in the dosing of study medication, completion of treatment response and adverse event rating scales, and procedures for serious adverse events. Subjects will receive written information on adverse effects of rizatriptan. Women of child bearing years will have a pregnancy test to confirm they are not pregnant.

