**4. Treatment Phase.** Subjects who qualify for randomization will enter the Treatment Phase. They will be randomly assigned to parallel study arms in a 2:1 ratio of rizatriptan 10 mg encapsulated tablets or look-alike placebo capsules. Subjects will treat three vestibular attacks that manifest with Grade 3/2 vestibular symptoms. Associated symptoms, including headache, need not be present and may be of lesser severity. Headaches without vestibular symptoms are not eligible for study treatment, but may be treated in the subjects' usual manner. Subjects will be instructed to ingest one study capsule as soon as possible after onset of Grade 3/2 vestibular symptoms. They will record treatment response in their Vestibular Symptom Diaries by rating the severity of vestibular and associated symptoms at the time they take study medication and at 0.5, 1, 2, 4, 24, and 48 hours post-dose. Subjects will record adverse effects in accordance with the Common Toxicity Criteria Scale 4.0, treatment satisfaction on the TSQM, and quality of life on the SF-12 at 48 hours post-dose. Then they will contact study personnel by phone to review the attack and treatment response.

Subjects will treat one attack with study medication in a 48-hour period. Repeat dosing of study medication within 48 hours will not be permitted. Subjects must have a vertigo-free period of at least 48 hours before treating a subsequent vestibular attack with study medication. The relatively short plasma half-life of rizatriptan (2-2.5 hours) justifies the 48-hour wash out period. Subjects may use other medications to treat residual symptoms (see Concomitant Medications) but must wait at least 1 hour after taking the study medication. Additional treatments will be reported to study personnel together with other attack data. Subjects will remain in the Treatment Phase until they have treated three separate vestibular attacks, experience serious or intolerable adverse effects, withdraw for other reasons, or reach the end of the study. Study personnel will conduct telephone assessments on a monthly basis as they did during the Observation Phase. Extra visits to study clinics will be arranged as needed to re-evaluate subjects' health and treat problematic symptoms.

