**3. Statistical Analysis and Modeling.** We will use SAS and R^70 statistical software, creating ad hoc algorithms and macro procedures to solve analytical questions for which no marketed algorithms exist.

1. As a first step to understanding the nature of our data, we will conduct univariate analysis of demographics, primary and secondary outcome measures, illness-related variables (e.g., frequency, severity, and duration of vertigo attacks), associated symptoms, comorbid conditions, and self-report rating scales. The marginal distribution of each measure will be calculated at each time point and across time. The time trends of outcome measures will be evaluated by graphical analyses. For example, parallel plots for each of the outcome measures will be created to examine the patterns of change over time.

2. We will test the four hypotheses of Specific Aim #1 using bivariate methods and multivariate modeling. First, we will analyze differences between rizatriptan and placebo on all outcome measures at each time point using chi-squares to cross-tabulate categorical variables, and t-tests, analyses of variance (ANOVAs), or marginal regressions to compare continuous variables.

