4. We will use this 3-step analysis procedure to test all outcome measures for hypotheses 1a-1d. However, the principal result of the study will be determined by the findings of bivariate analyses and multivariate modeling of the main outcome measure, 1.a.(1), plus favorable findings on tolerability measures, 1d(1)-1d(2). We will include all subjects who treat at least one vertigo attack with study drug (i.e., intent-to-treat analysis). A statistically significant result favoring rizatriptan over placebo on 1a(1) and absence of statistically significant differences on 1d(1)-1d(2) will support development of a Phase III clinical trial of rizatriptan for treating vestibular attacks in patients with VM. The design of future trials will also be informed by results of tests of secondary measures 1a(2)-1c(2). We did not hypothesize equal tolerability for rizatriptan and placebo, but rather an absence of significantly higher rates of serious adverse effects and drug-related treatment discontinuation, so our statistical analyses of measures 1d(1)-1d(2) will not include equivalence tests.

[figure not shown]

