5. Analyses of Specific Aim #2 (a-c) will be descriptive and exploratory. As a Phase II trial, this proposed study is not powered for a thorough examination of covariates and confounds. We will start by reviewing univariate analyses of data collected during the Observation Phase of the study to identify results that will be critical for designing future Phase III trials. First, we will examine the distribution of VM attack frequency and severity (2a) to determine if these variables have normal, skewed, bimodal, or other distributions. This will allow future investigators to estimate recruitment patterns for Phase III studies. Second, we will establish a rank order of comorbid conditions (2b) by prevalence and likelihood of affecting the clinical course or treatment of VM. This will allow future Phase III investigators to understand trade-offs between strictness of subject selection criteria and generalizability of results. Third, we will establish a rank order of usual care and self-medication therapies for VM (2c). This will allow future investigators to establish criteria for allowable co-treatments in Phase III trials. Finally, we will repeat the multivariate modeling of step 3 above, including variables representing data 2a-c collected during the Treatment Phase of the study. Variables found to have significant or trend level effects on rizatriptan versus placebo treatment will mark design considerations for Phase III trials and potentially generate hypotheses for epidemiologic, mechanistic, or other lines of investigation of VM.

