### **B. Procedures**

Study procedures are summarized Table 2 of the study protocol. The study involves three visits to the study sites, an Observation Phase and a Treatment Phase. At the Enrollment Visit, investigators will verify eligibility, obtain written informed consent, and gather initial data. Subjects will complete the self-report measures listed in Table 2. This visit is expected to last 2-3 hours. After the Enrollment Visit, subjects will enter up to a 12 month Observation Phase during which they will record descriptive data and ratings for each vertigo attack that they suffer, along with associated symptoms and treatments. The research coordinator will contact subjects on a monthly basis to review these data. Phone interviews are expected to last less than 30 minutes. During the Observation Phase, investigators will prospectively evaluate patients for comorbid medical and psychiatric conditions. Investigators will treat these conditions themselves or enlist the care of relevant medical specialists as indicated. Subjects may return to the study centers for ad hoc visits, if needed for additional evaluations. Subjects will continue in the observation period until they have two vestibular attacks that meet the inclusion criteria or until the 12 months are up.

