Once they have experienced two qualifying vestibular attacks or at the end of the Observation Phase, subjects will return to their study center for a second visit. Investigators will collect interval history and subjects will complete the self-report measures listed in Table 2. This visit is expected to last 2 hours. Subjects who experience at least two vestibular attacks of moderate or greater severity during the Observation Phase and demonstrate acceptable adherence with data gathering and reporting procedures will be randomized to treat three subsequent vestibular attacks with either rizatriptan or placebo (ratio 2:1) in randomized and double-blind fashion. Subjects will rate treatment response and adverse effects. They will contact study personnel to review these data at 48 hours after each vestibular attack treated with study medications. The research coordinator will contact subjects on a monthly basis by phone to review progress, assess adherence, and gather data on any interval change that might affect treatment response or safety. The Treatment Phase may last as short as 6 days for subjects who have three vertigo attacks in quick succession after randomization to as long as 4 years for subjects who enroll at the start of the study and do not have 3 treatable attacks before the end of the study. Subjects will return to the study site for an End Point Visit (visit 3) as soon as possible after treating three attacks or sooner if they will be withdrawn from the study for any reason. The End Point Visit is expected to last 2 hours.

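### Secondary outcome 1a(4), non-study therapy use per treated attack, has no pre-specified adjustment for the subject's own run-in therapy use, although that baseline is already collected

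*Combined protocol and SAP*

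**What the plan says.** **The outcome.** Section III (Approach) gives secondary outcome 1a(4) as "Use of fewer non-study therapies after each attack treated with study medication". It does not say whether this means a count or any use. Under III.D.4, "Subjects will treat three vestibular attacks that manifest with Grade 3/2 vestibular symptoms", so each subject contributes up to three treated attacks.

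**The run-in data.** For the Observation Phase, III.D.2 says of subjects: "They will record all interventions in their Vestibular Symptom Diaries". Section IV.B shows that this is done by attack: subjects are to "record descriptive data and ratings for each vertigo attack that they suffer, along with associated symptoms and treatments". The same section makes run-in attacks a condition of randomisation. Those randomised are "Subjects who experience at least two vestibular attacks of moderate or greater severity during the Observation Phase" who also keep up with data reporting.

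**The analysis.** III.J.3 item 4 states: "We will use this 3-step analysis procedure to test all outcome measures for hypotheses 1a-1d". Item 2, the bivariate step, uses chi-squares for categorical variables and "t-tests, analyses of variance (ANOVAs), or marginal regressions to compare continuous variables". No covariate is named. Item 3 fits mixed models. Its worked example, for vertigo severity, mentions illness-related variables, associated symptoms and rating scales, but then defines the fixed predictors as arm and time only. Item 5 repeats the modelling as an exploratory analysis, "including variables representing data 2a-c collected during the Treatment Phase of the study". Run-in therapy use is otherwise planned only for a descriptive ranking of usual-care and self-medication treatments.

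**The concern.** How readily a person reaches for a symptomatic drug is partly habit, and habits differ between people. The treatment contrast on 1a(4) is between subjects, so that variation goes straight into its standard error. A subject's own therapy use in run-in attacks is the natural covariate for removing part of it, and here it costs nothing to collect.

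The planned steps do not use it. The random subject effect in item 3 handles correlation among a subject's attacks, but it does not take between-subject variance out of a between-subject contrast. The medication data named in item 5 cannot stand in for a baseline: they are collected after randomisation, and part of them (therapies taken after treated attacks) is what 1a(4) measures.

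At stake is the precision of one superiority hypothesis in a trial planned with about 40 placebo subjects, and how easily a chance imbalance in rescue habits could blur it. The plan intends secondary results to inform later trial designs, so the precision has some use.

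**Working it through.** **1. The plan's own figure.** None is given for 1a(4). The only sizing, in III.J.1, is for 1a(1): 120 subjects at 2:1 (80 versus 40), two-sided 0.05, 80% power, detectable odds ratio 3.2. With a 22% placebo rate and odds ratio 3.2, the active rate is 3.2 × 0.22 / (0.78 + 3.2 × 0.22) = 47.4%. The pooled two-proportion formula then gives 79.0% power, 123 subjects for 80% power, and a smallest detectable odds ratio of 3.24 at 120 subjects. That agrees with the plan. It is used here only to fix the 80 versus 40 frame, and nothing below changes it.

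**2. Inputs for 1a(4).**
- At least b = 2 run-in attacks (IV.B) and up to m = 3 treated attacks (III.D.4).
- SD, mean count and correlation of therapy use: not in the documents, so assumed and varied.

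**3. Gain by subject-level correlation r** between mean run-in use and mean treated-attack use. Adjustment multiplies the residual variance by (1 − r²). For a comparison with 80% unadjusted power, 1.960 + 0.842 = 2.802, and

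adjusted power = Φ(2.802 / √(1 − r²) − 1.96).

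- r = 0.3: 83.6%
- r = 0.5: 89.9%
- r = 0.6: 93.8%

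The gain passes 5 points at about r = 0.35. The detectable standardised difference is 2.802 × √[(1 − r²)(1/80 + 1/40)], which is 0.54 SD unadjusted and 0.47 SD at r = 0.5.

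**4. What r might be.** Let ρ be the correlation between attacks of one subject within a phase, and λ the degree to which a subject's habit carries over between phases (1 = fully). Then

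r² = (λρ)² / { [(1 + (m − 1)ρ)/m] × [(1 + (b − 1)ρ)/b] }.

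Example with ρ = 0.3, λ = 1: 0.09 / (0.533 × 0.65) = 0.26.

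| λ | ρ | r² | SE relative to unadjusted | Power (from 80%) |
|---|---|---|---|---|
| 1 | 0.1 | 0.045 | 0.98 | 82% |
| 1 | 0.3 | 0.260 | 0.86 | 90% |
| 1 | 0.5 | 0.500 | 0.71 | 98% |
| 0.5 | 0.1 | 0.011 | 0.99 | 80% |
| 0.5 | 0.3 | 0.065 | 0.97 | 83% |
| 0.5 | 0.5 | 0.125 | 0.94 | 85% |

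With two treated attacks instead of three, the λ = 0.5 rows give 80%, 82% and 84%.

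**5. Check by simulation.** Poisson counts with subject effects were simulated for 120 subjects, with a mean of one therapy per attack and a rate ratio of 0.7 (all assumed). Power rose from 0.74 to 0.75 at an intraclass correlation of 0.09, from 0.47 to 0.59 at 0.30, and from 0.25 to 0.51 at 0.56. Neither analysis showed material bias.

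The formulas in steps 3 and 4 are normal-theory results for one mean per subject. For the count model recommended below they are approximations.

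**The case against.** **The gain may be close to nil.** This is the strongest objection, and it stands. A gain of about 10 points needs a correlation near 0.5, which in step 4 means ρ of about 0.3 with full carry-over between phases. The documents give reasons to doubt full carry-over:
- Run-in attacks are treated as usual. Under III.G, non-study therapy in the Treatment Phase starts only from 1 hour after dosing, and other triptans are barred within 48 hours of study medication.
- Comorbidities are managed and doses stabilised during the Observation Phase.
- Visit 2 follows the second qualifying attack, so many baselines would rest on about two attacks.
- The Treatment Phase can run for up to 4 years (IV.B), so some baselines will be old.

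**The plan does not rule adjustment out.** This also stands. Item 3 says covariate effects will be examined, its variable list is an example for another outcome, and illness-related variables are only illustrated (attack frequency, severity and duration). A reader might infer that the plan forbids the adjustment. The text supports only that it is unspecified, which leaves the choice of covariates open until data are seen.

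**The Treatment Phase medication data are not simply the outcome.** That is correct. Aim 2c covers types, doses and frequency of all medications for vestibular migraine, including preventives held at stable doses. Only the part used after treated attacks overlaps 1a(4). The data are still post-randomisation and cannot serve as a baseline.

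**The consequence is small.** III.J.1 says secondary outcomes need not be powered, and item 4 rests the principal result on 1a(1) and the tolerability measures. The results summary attached to the plan does not list therapy use among its secondary outcomes. All of this limits the weight of the point. None of it supplies the missing covariate.

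**Conclusion.** The point holds as one of precision. Run-in therapy use is available for every randomised subject, and no planned analysis of 1a(4) names it as a covariate.

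A reader might go further and infer that the 1a(4) comparison is biased, or that the trial misses a stated power. Neither follows. Randomisation keeps the unadjusted test valid, its standard error already covers chance imbalance, and no power was stated for this outcome.

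Nor can one figure be given for the loss. From 80% unadjusted power, adjusted power is about 80-85% if cross-phase agreement is weak (λ = 0.5, ρ from 0.1 to 0.5), and about 84-94% if the subject-level correlation is 0.3 to 0.6. These rest on assumed correlations, 80 versus 40 subjects, and in the first case two run-in and three treated attacks each. It is an inexpensive improvement worth making, and it leaves the primary outcome and its sample size untouched.

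**What to change.** In III.J.3 items 2 and 3, pre-specify for 1a(4):
- **Outcome:** the number of non-study therapies per treated attack, stated to be a count.
- **Model:** a count model with log link, reporting a rate ratio. Fixed effects are treatment and the subject's mean number of therapies per qualifying run-in attack, from the Observation Phase diary. Allow for clustering of attacks within subject.
- **Beside it:** the unadjusted rate ratio from the same model form.

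The link should be fixed in advance. With an ordinal logit, adding a covariate changes the odds ratio being estimated as well as its standard error, so adjusted and unadjusted results would not be comparable. With a log link and a randomised treatment, both target the same rate ratio.

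The cost is a short addition to the analysis plan and one derived covariate, with no new data. If run-in and treated-attack use correlate weakly, little is gained.

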## **K. Timeline of Study**

During the first three months of the study, we expect to finalize data entry methods and train study personnel. Then we will begin recruitment into the Observation Phase. Patients will remain in the Observational Phase until they have two qualifying attacks or for a maximum of 12 months. These phases will continue for a total of four years. Subjects who are active in the Treatment Phase at month 57 will be scheduled for a Final Visit (Visit 3) regardless of how many attacks they have treated. We will conduct reviews every 3 months to evaluate enrollment and the flow of subjects through all parts of the study to determine whether recruitment efforts have to be extended and to examine safety data with the DSMB. Analysis of data from the Observation Phase will begin as soon as that portion of the study is closed. Interim analysis will occur at month 33. Analysis of treatment outcome data will commence after the last subject has a Final Visit.

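### Observation ends at each subject's second qualifying attack, and the planned summaries of attack frequency (Aim 2a) make no allowance for that stop

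*Combined protocol and SAP*

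**What the plan says.** Section III (Approach) gives the purpose of Aim 2a: "Our goal is to identify the mean, median, and range of naturally occurring vestibular attacks in patients with VM", to help later investigators size and time their trials. The Specific Aims make the same link between Phase III planning and the natural history of attacks.

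The analysis is in III.J.3, item 5: "We will start by reviewing univariate analyses of data collected during the Observation Phase of the study". On frequency it adds: "First, we will examine the distribution of VM attack frequency and severity (2a) to determine if these variables have normal, skewed, bimodal, or other distributions".

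The length of observation is set in two places. III.K says "Patients will remain in the Observational Phase until they have two qualifying attacks or for a maximum of 12 months". IV.B says "Subjects will continue in the observation period until they have two vestibular attacks that meet the inclusion criteria or until the 12 months are up".

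The diary is wider than the stopping rule. Under III.D.2, "Subjects will record data about all vestibular attacks that they experience during this period in their Vestibular Symptom Diaries". Qualifying attacks are a subset: at least 2 hours long (inclusion criterion b) and of at least moderate severity (IV.B).

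No section defines the frequency measure as a count, a per-subject rate, a pooled rate or a time to attack. The missing-data text (III.J.3, item 6) does not deal with observation that ends on an event.

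**The concern.** Observation time is decided by the outcome that Aim 2a wants to describe. A subject with 2 qualifying attacks a year and one with 20 a year can both leave with two; only the time taken differs. A plain summary then goes wrong in a way that depends on which summary is chosen:

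- Counts of qualifying attacks cannot show how active the frequent attackers are.
- Attacks divided by time observed is too high on average, because the clock stops at an attack.
- Total attacks over total time gives little weight to frequent attackers, because they contribute little time.

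At stake is the use that Aim 2a names. A mean attack rate that is too high or too low would carry over into the size and duration of the trials that rely on it.

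**Working it through.** The documents state no attack-frequency figure, so there is none to reproduce. The check asks what simple summaries return when the truth is known.

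**Inputs from the documents.** Stop at the second qualifying attack or at 12 months (III.K, IV.B). Share reaching two attacks: 50% expected (III.L); 114/225 = 50.7% in the results summary at the end of the document. The latter is used for calibration.

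**Assumptions.** Attacks follow a Poisson process with yearly rate L, constant within subject. Between subjects, L is either equal or gamma-distributed with shape k and scale θ. T is the time of the second qualifying attack in years.

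**Calibration.** With equal rates, P(two attacks within a year) = 1 − e^(−L)(1 + L). At L = 1.70 this is 1 − 0.183 × 2.70 = 0.507.

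**Counts.** Expected observed count = 2 − 2e^(−L) − L·e^(−L) = 2 − 0.365 − 0.311 = 1.32, against a true 1.70.

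**Mean of per-subject rates.** Subjects stopped at the second attack contribute 2/T, with expectation 2L(1 − e^(−L)). Subjects with one attack in 12 months contribute 1, with expectation L·e^(−L). The sum is L(2 − e^(−L)), so the ratio to the truth is 2 − 0.183 = 1.82. With gamma rates the ratio is 2 − (1 + θ)^−(k+1). For k = 1 and θ = 2.47 it is 2 − 3.47^(−2) = 1.92. Without the 12-month cap it is exactly 2.

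**Pooled rate.** For k = 1, mean count = 2 − 2/3.47 − 2.47/3.47² = 1.22. Mean time = [2·ln(3.47) + 1/3.47 − 1]/2.47 = 0.72 years. The pooled rate is 1.22/0.72 = 1.69, and 1.69/2.47 = 0.69.

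**Results.** The closed forms agree with simulation (2,000,000 subjects per scenario).

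| Rates between subjects | True mean per year | True 95th percentile, 12-month count | Observed mean count (max 2) | Mean of per-subject rates ÷ true mean | Pooled rate ÷ true mean | Median per-subject rate ÷ true median |
|---|---|---|---|---|---|---|
| Equal | 1.70 | 4 | 1.32 | 1.82 | 1.00 | 1.19 |
| Gamma, k = 2 | 2.04 | 6 | 1.26 | 1.88 | 0.83 | 1.19 |
| Gamma, k = 1 | 2.47 | 8 | 1.22 | 1.92 | 0.69 | 1.20 |
| Gamma, k = 0.5 | 3.77 | 15 | 1.16 | 1.96 | 0.46 | 1.21 |

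The median count, 2, is the same with and without the stop in all four rows.

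**All diary attacks.** If a share q of attacks qualifies and the rest arise independently, the ratio becomes 1 + q(R − 1), where R is the qualifying-attack ratio. With q = 0.5 the range is 1.41 (1 + 0.5 × 0.82) to 1.48 (1 + 0.5 × 0.96). With q = 0.25 it is about 1.21 to 1.24. The pooled ratios stay as in the table.

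**Diary kept until Visit 2.** Simulated ratios for the mean of per-subject rates are 1.41 to 1.56 with a 14-day lag and 1.27 to 1.40 with 30 days (gamma scenarios only). The shares and lags are assumptions; the documents give neither.

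**Spread.** The variance of 2/T is infinite in this model. In samples of 240 with k = 1, the ratio for the mean of per-subject rates ran from 1.40 to 2.80 (95% of samples).

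**A correction that works.** Use 1/T for subjects stopped at the second attack and N/time for the rest. The expectation is L(1 − e^(−L)) + L·e^(−L) = L, so the ratio is 1.00 for any mix of rates. The same algebra holds with a drop-out time in place of one year, if drop-out is unrelated to attacks.

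**The case against.** The strongest reply is that the plan commits to no biased estimator. Item 5 only says that the distribution will be examined. The diary covers every attack, and Visit 2 follows the second qualifying attack at no fixed interval. A reader might infer that all recorded counts stop at two and that the reported rate will be about double. The documents do not support this. Only qualifying counts are cut, and doubling belongs to one summary, the unweighted mean of per-subject qualifying-attack rates, which the plan never names. That part of the reply stands. It does not remove the problem, because the obvious summaries of the mean err in opposite directions and the choice is left open.

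A second reply is that the share reaching two attacks within 12 months, and the time taken, can be observed directly under this rule. A later trial with a similar run-in could use them without any rate. This is correct, and it is why time-to-attack curves belong in the fix. Aim 2a nevertheless promises a mean, median and range.

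Treatment Phase data do not fill the gap. They come only from subjects who already had two attacks, that phase stops at three treated attacks, and its stated use for these data is exploratory analysis of efficacy.

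A third reply concerns the remedy: a gamma-Poisson model that recovers data generated from itself proves little. In simulations that break its assumptions, the fitted mean was 3.7 against a true 4.8 (lognormal rates, sigma 1.5) and 2.3 against 2.0 (waxing and waning rates). This stands as a limit on any single model.

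A reader might also infer that this repeats the failure of the earlier zolmitriptan trial. Section II.A does not say so. It points to insufficiently active patients, the lack of prospective observation, and too few attacks per subject and centers, not to a biased attack rate.

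**Conclusion.** The concern holds as a defect in the analysis of a secondary, descriptive aim. The stop depends on the outcome, the planned summary is univariate, and no allowance is made. With about half of subjects reaching two attacks, the ratios to the truth are:

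- mean of per-subject qualifying-attack rates: about 1.8 to 2.0;
- the same mean with all diary attacks, or with the diary kept to Visit 2: about 1.2 to 1.6;
- pooled rate: 1.00 with equal rates, down to about half with very unequal rates;
- median per-subject rate: about 1.2.

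The upper range of qualifying counts is lost. These sizes rest on Poisson attacks, a constant rate within subject, the assumed spread between subjects, and the assumed qualifying shares and lags. The primary test is not affected.

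**What to change.** In III.J.3, item 5, replace the plain univariate summary of attack frequency with estimates that allow for the event-driven stop. Use all enrolled subjects, and keep 12-month non-qualifiers and drop-outs as censored.

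1. Report Kaplan-Meier curves for time to first and to second qualifying attack.
2. For the mean rate of qualifying attacks, use 1/T for subjects stopped at the second attack and N/time for the others. Alternatively or in addition, fit a Poisson model with a between-subject rate distribution, using count and time at risk, to qualifying attacks and to all diary attacks. Add a sensitivity analysis on the assumed distribution.
3. Raw counts and attacks/time may still be shown, labelled as affected by the stopping rule.

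No visit, eligibility or treatment rule changes, and the diary dates are already collected. The cost is a little more analysis. The 1/T estimate is unbiased only for a constant rate within subject, and it keeps the heavy tail of 2/T, so its sampling error can be large. The model's mean and percentiles depend on the assumed rate distribution and on the same constant-rate assumption.
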